2.3 RISK/BENEFIT ASSESSMENT

2.3.1 KNOWN POTENTIAL RISKS

- 1) Risk of boredom or fatigue (likely). Participants may become tired or bored during the intervention, assessments, and computerized cognitive testing.

To minimize risk: Participants will be allowed breaks in between testing sections and game-play is completed for no more than 25 minutes/day.

- 2) Loss of confidentiality around sensitive information (rare).

To minimize risk: All subjects are assigned research numbers, and all research information collected is linked to the subject only by this number. Great care is taken to remove all identifying information from research records. A single tracking file contains links to the research records and subject codes. Recruitment tracking files are kept only for the duration of recruitment. Any paper records are kept in locked file drawers in a locked room, to which only authorized research personnel have access. Any paper records with identifying information (consent form, payment records) are kept in locked file cabinets, physically separate from the research records. Computer records with identifying information are kept on secure, password protected servers. Staff members are trained to scrupulously protect the confidentiality of sensitive information, and take care to limit the printing of documents with identifying information and to avoid unnecessary discussion of subject names. Screening forms for subjects who do not qualify for the study will be destroyed, except for anonymous information unlinkable to the subjects (such as age, gender, and education).

However, if a subject may become eligible in the near future, e.g. they need to wait 1 month after a recent medication change, we will retain certain records so as not to repeat the assessments, with the assent of the potential participant.

- 3) Worsening of depressive symptoms, including suicidal thoughts plans, intentions or behaviors.

Depressive symptoms may worsen during the course of the participation in the study, including the emergence of suicidality. During the screening period in Assessment 1, suicidal thoughts, plans, intentions and behaviors will be assessed with the Columbia-Suicide Severity Rating Scale – Screen Version (C-SSRS). If assessment uncovers suicidal plans or intentions or recent behaviors, emergency evaluation will occur, and an appropriate plan of action will be followed, e.g. safety plan will be created and referral to psychiatric emergency room. Subjects will not continue to be enrolled in the study if any items on the C-SSRS are endorsed during the screening period of Assessment 1. Therefore, any potential participant with suicidal thoughts or behaviors will be excluded from the study. Suicidal thoughts will also be assessed after the 4-week intervention and (if applicable) at a 3-month follow up through items on the CDI and CDSRS. If these items are endorsed, then evaluation will occur, followed by an appropriate plan of action (as stated above). If symptoms worsen during the course of participation, but not to the level of suicidal thoughts, plans, intentions or behaviors, the participant may be withdrawn (see 7.1 below).

2.3.2 KNOWN POTENTIAL BENEFITS

For all participants, there is a potential benefit from the CCT intervention. For those who may have previously received CBT, there is an added potential benefit from the effect of combined therapy and cognitive control training (CCT). It is also possible that participants may not derive any direct benefit from participating in the study. Please refer to *section 2.2.3* for additional information about potential benefit from the CCT intervention.

2.3.3 ASSESSMENT OF POTENTIAL RISKS AND BENEFITS

The risks associated with this study are no greater than those associated with usual clinical management of subclinical depression and anxiety in children and adolescents. The proposed experiment could reveal important information about the nature of mental processes involved in the pathophysiology of subclinical depression and anxiety. It is expected that this information may indirectly lead to the development of better forms of preventative intervention for depression and for treatment for anxiety and/or depression. There is no other, safer or less-invasive means of answering the questions posed by the experiment described above. Strategy has been made to minimize each risk, respectively.

3 OBJECTIVES AND ENDPOINTS

OBJECTIVES	ENDPOINTS	JUSTIFICATION FOR ENDPOINTS	PUTATIVE MECHANISMS OF ACTION
Primary			
To examine the efficacy of CCT in reducing depressive and anxiety symptoms and improve cognitive control.	Depressive symptoms and cognitive control behavioral performance after the intervention.	We anticipate that CCT will result in increased cognitive control capacity, which will also relate to reductions in depressive symptoms.	Enhanced cognitive control ability (as trained with CCT) will improve the ability to regulate symptoms, thus lowering symptoms and reducing risk of developing full disorder.
Secondary*			
To examine the durability of change in depressive symptoms and cognitive control 3-months after the CCT intervention.	Depressive symptoms and cognitive control capacity 3-months post-intervention.	We anticipate that depressive symptoms will be reduced, and cognitive control enhanced, to a greater extent 3-months post-intervention as compared to immediately post-intervention.	Changes in cognitive control that may also support a reduction in depressive symptoms may have solidified over 3-months and therefore become detectable in self-report and clinician-administered assessments.
Feasibility/Acceptability and Experimental Outcomes			
1) To assess whether participants engage in the intervention as instructed.	1) Game-play metrics provided by Akili software; 2) ESS scores from	1) We anticipate that participants will play the game as instructed, 2) that they will have	Prior studies of EndeavorRx have demonstrated the feasibility and

OBJECTIVES	ENDPOINTS	JUSTIFICATION FOR ENDPOINTS	PUTATIVE MECHANISMS OF ACTION
2) To assess whether participants enjoy engaging in the intervention. 3) To examine whether the effects of CBT in the Parent study have been maintained at a 2-year follow-up.	each post-intervention assessment; 3) Depressive symptoms at Assessment #1 of current study	favorable emotions associated with game play and, 3) that depressive symptoms will still be reduced from the original baseline assessment, but that they will be greater than they were immediately after intervention in the Parent study.	acceptability of the intervention. Also, that treatment for anxiety disorders in the Parent study should also reduce co-morbid depressive symptoms, and that this reduction should be maintained over time.

4 STUDY DESIGN

4.1 OVERALL DESIGN

We hypothesized that cognitive training *EndeavorRx* may augment cognitive control and reduce depressive symptoms. In this study, youth with subclinical depressive symptoms (ages 9 to 17) will be recruited to complete the CCT intervention for 4-weeks. Before and after the intervention, all participants will complete semi-structured clinical assessment of depressive symptoms and a computerized evaluation of cognitive control capacity (e.g., Millisecond Inquisit Web Cognitive Battery; Zelazo, Anderson, Richler, Wallner-Allen, and Beaumont, 2013)

Recruitment will leverage a well-characterized sample from a recently completed study (“Parent study”; HUM00118950) of clinically significant anxiety, a known risk factor for emergence of later depressive symptoms in the subclinical-to-clinical range. In the Parent study, 148 youths (7-17 years) with impairing anxiety were recruited and randomized 2:1 to receive 12-week CBT or a non-active control therapy, “relaxation and mentorship therapy” (RMT); behavioral, neurobiological (fMRI), and clinical measures were collected before and after treatment. Additional participants may need to be recruited beyond the “Parent study” sample (for reasons such as: slow recruitment from “Parent study” or not enough participants from “Parent study” meeting enrollment criteria).

Up to thirty subjects from the Parent study will be recruited to complete the *EndeavorRx* intervention. The intervention will be played at home for ~25 min/day), 5x per week, for 4 weeks. Designed as an exciting, youth-friendly computer game, *EndeavorRx* engages and trains cognitive control across component processes of attention, response inhibition, shifting and working memory. Of note, *EndeavorRx* game difficulty is titrated to individual performance, and thus age; the increasing difficulty helps to reduce participant boredom and progressively train cognitive control. Adherence to prescribed training will be monitored using an Akili-provided dashboard, available to the research study team, that interfaces real-time as participants access *EndeavorRx* via their iPads. If there is no game play for ≥48 hours, a parent will be contacted in order to ensure compliance with the intervention.

If the Parent study does not yield sufficient participation, then we will recruit through the community using the social media campaign strategies that have proven effective in our past work, including UMHealthResearch. The proposed study will add up to three additional timepoints of assessment (pre-intervention, post-intervention, and (if applicable) 3-months post-intervention. All study activities will be completely remotely via an encrypted HIPAA-compliant video conferencing platform (e.g., Zoom), phone

call, and/or Qualtrics links. Depressive symptoms, anxiety symptoms, general psychopathology, and cognitive control behavior as indexed by a *Millisecond Inquisit Web* Cognitive Battery will be assessed pre-intervention. After the intervention, the same symptoms and cognitive control behavioral will be assessed. These variables will optionally be assessed again 3-months post intervention.

Data analyses will compare pre- and post-CCT data. Additionally, multilevel models will assess change in depressive symptoms and cognitive control over time and comparing between those who received CBT as compared to those who received RMT in the Parent study. These data will include *Millisecond* measures of behavioral capacity for cognitive control and detailed assessment of depressive and anxiety symptoms using both clinician-interview and self-report. Pre- to post-CCT change in depressive symptom severity (clinician-measured) will serve as the primary outcome variable.

At protocol version 2.1 (02 April 2024), Assessment #3 (3-month follow-up) was removed to increase feasibility so that resources could focused on increased recruitment.

4.2 SCIENTIFIC RATIONALE FOR STUDY DESIGN

We hypothesize that CCT will improve cognitive control capacity and thereby reduce depressive symptoms post-intervention and (if applicable) after a 3-month period post intervention. Therefore, we will enroll youth with subclinical depressive symptoms to complete the CCT intervention and measuring their cognitive control capacity and clinical symptomology after the intervention.

The aims of this project are to:

1. Examine whether CCT will reduce depressive and anxiety symptoms and improve cognitive control after the 4-week intervention.
2. If applicable, examine whether the effects of CCT change in a 3-month period after the CCT intervention.
3. Examine the feasibility and accessibility of the CCT intervention.
4. If applicable, examine whether the effects of cognitive behavioral therapy (CBT) in a previous intervention and protocol have been maintained at a 2-year follow-up.

4.3 JUSTIFICATION FOR INTERVENTION

The CCT intervention will consist 4-weeks of video game play (for 25 minutes/day, 5 days/week). The *EndeavorRx* video game is designed to target focused attention, response inhibition, working memory and multiple simultaneous attention to constitute a general executive function training, and activate neural systems associated with executive function/cognitive control. All video game play will be done remotely, at-home, via iPad. iPads will have *EndeavorRx* preloaded or downloaded onto a personal iPad, which participants will access through a unique username and password. Difficulty of the games will be titrated individually and by session to avoid boredom and progressively activate the functional systems underlying cognitive control, which we hypothesize will subsequently reduce depressive symptoms. Prior clinical trials have administered *EndeavorRx* for this duration and frequency (4 weeks, 25 minutes/day, 5 days/week) in youth (Kollins et al., 2020).

4.4 END-OF-STUDY DEFINITION

A participant is considered to have completed the study if he or she has completed the baseline assessment, at least 4 weeks of CCT intervention, *Millisecond* battery, post-intervention assessment, and

the final assessment. If a participant completes all these activities but not the final, optional (3-month post-intervention) assessment, then they will, at PI discretion, still be considered to have completed the study. In other words, if a participant does not participate in Assessment #3, they will still be considered to have completed the study. At protocol version 2.1 (02 April 2024), Assessment #3 (3-month follow-up) was removed altogether.

5 STUDY POPULATION

5.1 INCLUSION CRITERIA

In order to be eligible to participate in this study, an individual must meet the following criteria:

1. Parent or guardian willing to give informed consent, and children willing to give informed assent to participate in the study.
2. Males and females (age 9 – 17.99)
3. Participant is willing to engage in a technology-based intervention (technology will be provided to participants who live in the state of Michigan, if not already accessible to participant).
4. Self-reported depressive symptoms (CDI score between 3-19 at Assessment 1)
5. Participants will be required to maintain a stable dose of medications for 4 weeks prior to the first assessment and stable medication throughout the intervention period. Participants may change medication after completion of the post-intervention assessment (i.e. in between the post-intervention assessment and follow-up assessment).

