6.3 MEASURES TO MINIMIZE BIAS: RANDOMIZATION AND BLINDING

There is no randomization in this pilot study.

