6.4 STUDY INTERVENTION/EXPERIMENTAL MANIPULATION ADHERENCE

Tolerability and compliance with the intervention will also be assessed. The CCT application will measure the amount of time each day that the child spends playing the video game. Additionally, completion of self-report questionnaires and *Millisecond* assessments will be tracked to ensure that these assessments are completed within the specified time period. If the cognitive task battery and start of the cognitive training intervention are not completed within sufficient time of the baseline clinical and self-report assessment (i.e., within 14 days of completing the CDI; due to scheduling and/or equipment constraints), then the CDI and CDRS-R will be re-administered prior to initiating the cognitive task battery and cognitive training.

Assessments will include (refer to 1.3 Schedule of Activities for a list of which measures are completed at each assessment):

Assessments by Clinician

- a) C-SRSS
- b) CDRS-R
- c) K-SADS

Assessments Completed by Subjects

- a) MASC
- b) CDI
- c) SCARED (parent)
- d) CBCL (parent)
- e) ERQ-CA

Other Assessments

- a) ESS (parent and child)

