8.2 SAFETY ASSESSMENTS

Safety assessments include the following:

- **Columbia Suicide Severity Rating Scale** (C-SSRS), Screen Version - Recent (Posner, Oquendo et al. 2007). A clinician-rated scale assessing suicidal ideation and behavior.
- **Child Depression Inventory** (CDI). A self-report assessment to rate the severity of depression symptoms in children. Total scores on this measure range from 0 to 54. Symptom worsening: > 25% increased CDI score (referenced to baseline).

Any safety-related assessments (C-SSRS administered at Assessment #1) or primary outcome measure (CDI at Assessments #1 or #2) that are missed will be reported to the IRB as a protocol deviation. We will accept a window of \pm 1 week. However, for the other assessments, missing or late assessments will not be reported as protocol deviations unless they constitute > 50% of the total assessments. These allowances should affect neither the scientific integrity nor the safety monitoring provisions of the protocol.

All SAEs will be:

- recorded on the appropriate SAE Report Form
- followed through resolution by a study clinician
- reviewed and evaluated by a study clinician.

The study will comply with IRB reporting requirements and guidelines for SAEs.

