9.4 STATISTICAL ANALYSES

9.4.1 GENERAL APPROACH

Data will be analyzed using statistics software such as SPSS and R software. For descriptive statistics, means with standard deviation and range will be computed for continuous data (all behavioral data and some of the clinical data). In general, statistical significance is reported based on $p < 0.05$ two-tailed. Missing data from Assessment 3 (if applicable) will be handled using pairwise deletion. Missing data from Assessment 1 or 2 will be handled using listwise deletion.

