9.4.2 ANALYSIS OF THE PRIMARY ENDPOINT(S)

We hypothesize that CCT will increase cognitive control capacity and reduce depressive symptoms. The hypothesis will be tested using paired samples (repeated measures) t -tests (pre vs. post) for each dependent variable (CDI score and Millisecond battery composite score). Both of these dependent variables are interval variables.

Standard deviations and effect sizes will be assessed for each of these analyses.

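### The CDI reading that admits a child (3-19) is by default also the 'pre' score in the uncontrolled primary test, so selection alone can shift mean CDI in a direction the documents do not let us predict

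*Combined protocol and SAP*

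**What the plan says.** - **Entry (5.1).** A child must have "Self-reported depressive symptoms (CDI score between 3-19 at Assessment 1". The window is bounded on both sides.
- **Primary test (9.4.2).** Paired t-tests, "pre vs. post) for each dependent variable (CDI score and Millisecond battery composite score". Section 9.4.1 adds that "statistical significance is reported based on $p < 0.05$ two-tailed".
- **Status of the CDI.** Section 8.2 speaks of the "primary outcome measure (CDI at Assessments #1 or #2". Section 4.1 says something different: "Pre- to post-CCT change in depressive symptom severity (clinician-measured) will serve as the primary outcome variable". Section 9.1 names both the CDI and the CDRS-R in the primary hypothesis.
- **Control (6.3).** "There is no randomization in this pilot study". There is one arm.
- **Repeat CDI (6.4, and the footnote to the schedule in 1.3).** If the battery and the start of training are not completed within 14 days of the CDI, "then the CDI and CDRS-R will be re-administered prior to initiating the cognitive task battery and cognitive training". The plan does not say whether the repeat replaces the entry score as 'pre', or whether the 3-19 window is applied again.
- **Interim look (9.4.6).** Mean CDI at Time 2 is compared with mean CDI at Time 1.

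The plan describes no separate baseline, run-in or adjustment for regression to the mean.

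**The concern.** A single CDI reading is the child's usual level plus error. Children just above 3 include some whose reading was high by chance, and they tend to fall next time. Children just under 19 include some whose reading was low by chance, and they tend to rise. If that reading is also the baseline, the expected change under no effect is zero only where the two pulls cancel. With no concurrent arm, nothing in the analysis subtracts the remainder.

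Three uses of the data are exposed: the primary test against zero, the effect sizes that section 9.2 intends to pass to larger studies, and the comparison in 9.4.6, where the same shift could mimic or mask worsening. Natural course and practice also confound a single-arm change, but this artefact comes from the entry rule and can be dealt with inside the single-arm design.

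**Working it through.** **Inputs from the documents:** window 3-19 (5.1); scale 0-54 (8.2); paired t-test (9.4.2); two-sided 0.05 (9.4.1); target n=30 (9.2). **Not given, so assumed:** the recruitment pool's CDI mean and SD, and retest reliability r. Shifts are post minus pre, with no treatment effect.

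**1. The plan's own figure.** Section 9.2 states 80% power at 32 but gives no effect size, so 32 cannot be derived from it. If d=0.5 is assumed, ((1.960+0.842)/0.5)² = 31.4, rounded up to 32; the exact paired t-test needs 34. At n=30, 80% power needs d=0.529.

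**2. Mechanism by formula (normal scores).** Expected shift = -(1-r) × (mean of scores inside the window - pool mean), with the window taken as 2.5 to 19.5.
- Pool mean 5, SD 5, r=0.7: mean inside the window 7.51; shift = -0.3 × (7.51-5) = -0.75. The variance inside the window is 11.69, so the SD of change is √(0.3²×11.69 + 25×(1-0.7²)) = √13.80 = 3.71 and d = 0.75/3.71 = 0.20. Two-sided rejection at n=30 is 18.9%.
- Pool mean 11, the window's midpoint: shift 0, rejection 5.0%.
- Pool mean 15, SD 8, r=0.7: mean inside the window 12.27; shift = -0.3 × (12.27-15) = +0.82, rejection 11.4%.

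**3. Skewed scores, two error models (simulation).** True scores are gamma with variance r×SD². Error is normal with average variance (1-r)×SD², either constant or rising with the true score. Readings are rounded, clipped to 0-54, and kept if the first is 3-19. One-directional rejection comes from the noncentral t at n=30 (nominal 2.5%). Results at r=0.7:

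| Pool mean/SD | Constant error: shift, false reduction | Rising error: shift, false reduction |
|---|---|---|
| 5/5 | -0.90, 27% | -0.65, 13% |
| 8/7 | -0.70, 11% | -0.25, 4% |
| 10/7 | -0.31, 5% | +0.10, below 2.5% |
| 14/8 | +0.45, under 1% | +0.79, under 1% |

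With constant error, pool 11/7 gives -0.11 (3.3%) and 12/7 gives +0.08 (2.1%). Over r=0.6-0.8 the extremes are about -1.1 points with 30% false reduction (5/5, r=0.6, constant error) and about +1.0 points with 13% false worsening (14/8, r=0.6, rising error).

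**4. Other assumptions give wider limits.** The normal model at mean 5, SD 8, r=0.6 gives -1.65. A negative binomial model at mean 16, SD 8, r=0.6 gives +1.67, with 29% false worsening.

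**5. A repeat not used for selection.** In the negative binomial model at r=0.7, taking a second pre-training CDI as 'pre' brings the shift within 0.01 points of zero, with two-sided rejection of 4.8% (pool 5/5) and 5.0% (13/8). If only half the children have a repeat and it is used, half the shift stays: 0.48 becomes 0.24 at 5/5, and 0.90 becomes 0.45 at 13/8.

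**6. If the errors are not independent.** Assume half the error variance is mood state with a 14-day half-life, and the post reading is at day 60. At pool 5/5 (constant error, r=0.7) a near-immediate repeat leaves -0.39 points (8% false reduction), and a repeat 7 days after entry leaves -0.27 (6%).

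**The case against.** Four points count on the other side.

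- **Direction and certainty.** A reader might infer that selection necessarily produces a fall, or that the t-test has certainly lost its 5% level. The documents do not support either. The window cuts both tails, and for pools near mean 10-11 the pulls almost cancel.
- **Size.** A reader might take the 27% false-reduction rate as the expected figure. It needs a mild pool (5/5) and error of equal size at every score; letting error grow with the score halves it to 13%. It also fits the documents least: section 5.5 says recruitment is mostly from Parent-study youth who had endorsed elevated symptoms, with community recruitment as a fallback. The depression and suicidality exclusions in 5.2 may thin the upper tail further, which none of the models includes.
- **Which outcome is primary.** If the clinician-rated outcome in 4.1 governs, selection on the CDI reaches it only indirectly. This stands until the sections are reconciled. However, the only primary symptom test actually specified, in 9.4.2, is on the CDI.
- **Purpose.** This is a non-randomised pilot, and its p-value would not establish efficacy even with a clean baseline. That is true, but section 9.2 wants effect sizes from it, and a selection-shifted estimate would be carried forward.

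**Conclusion.** The concern holds as a possible bias of unknown direction. By default one reading both selects the child and serves as baseline in an uncontrolled paired test, and the plan does not say which CDI is 'pre' when two exist. Under the assumed pools the shift is about -1.1 to +1.0 points, with false reduction from under 1% to about 30% and false worsening up to about 13%, against 2.5% in each direction. It is near zero for pools around mean 10-11. These sizes rest on assumed pool means, SDs, reliabilities and error models, none of which the documents supply, so no single figure should be quoted as the trial's error rate. Nor can the sponsor assume that the two cut-offs cancel.

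**What to change.** 1. Use the Assessment 1 CDI for eligibility only.
2. Extend the 6.4 re-administration of the CDI to every child, shortly before the first training session. Do not apply the 3-19 window to this repeat, because that would bring the selection back. This concerns the entry window only; the safety handling of CDI responses in 8.1 is untouched.
3. Define the repeat as 'pre' in 9.4.2, and state which CDI is the Time 1 value in 9.4.6.
4. For children already treated, state before analysis which CDI is 'pre'. Show the change separately for those with and without a repeat, as a descriptive sensitivity analysis only: the groups will be small, and repeats arise from scheduling or equipment delays, so the groups may differ.
5. Reconcile the primary outcome between 4.1 (clinician-measured) and 8.2 and 9.4.2 (CDI).

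The repeat removes the artefact if errors at the two pre-training readings are independent, and reduces it otherwise. Natural course and practice effects remain. The cost is a short amendment and one extra online questionnaire, about 5 minutes by section 8.1, for each child not already repeating it. No new staff are needed.
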